Abbreviations: ACQ = Asthma Control Questionnaire; BSA = body surface area; CDLQI = Children's Dermatology Life Quality Index; C-SSRS = Columbia Suicide Severity Rating Scale; DLQI = Dermatology Life Quality Index; EASI = Eczema Area and Severity Index; ECG = electrocardiogram; EOS=End of Study; EOT = End of Treatment; ET= early termination; EQ-5D-5L = EuroQol Quality of Life 5-Dimension 5-Level Scale; EQ-5D-Y = EuroQol Quality of Life 5-Dimension, Youth Scale; FACIT-F = Functional Assessment of Chronic Illness Therapy Fatigue Scale; FSH = follicle stimulating hormone; GGT = gamma-glutamyl transferase; HADS= Hospital Anxiety and Depression Scale; HBsAg = hepatitis B surface antigen; HBsAb = hepatitis B surface antibody; HBcAb = hepatitis B core antibody; HBV DNA = hepatitis B virus deoxyribonucleic acid; HCVAb = hepatitis C antibody; HCV RNA = Hepatitis C Viral RNA; Hep B = Hepatitis B; HIV = human immunodeficiency virus; HSV-1 = herpes simplex virus type 1; HSV2 = herpes simplex virus type 2; IGA = Investigator's Global Assessment; IgE = Immunoglobulin E; IRT = Interactive Response System; LDH = Lactate dehydrogenase; LLQ = lower limit of quantification; MCH = mean corpuscular hemoglobin; MCHC = mean corpuscular hemoglobin concentration; MCV = mean corpuscular volume; NK = Natural Killer; NRS = numerical rating scale; Peds-FACIT-F = Pediatric Functional Assessment of Chronic Illness Therapy Fatigue Scale; PHQ-8 = Patient Health Questionnaire 8 items; POEM= Patient-Oriented Eczema Measure; PSAAD=Pruritus and Symptoms Assessment for Atopic Dermatitis; PtGA = Patient Global Assessment; RBC = Red blood cell; RNA = Ribonucleic acid; SBQ-R = Suicide Behaviors Questionnaire-Revised; SCORAD = SCORing Atopic Dermatitis; SF-36v2 = Short Form-36 Health Survey Version 2;VZV = varicella zoster virus; VZV IgG Ab = varicella zoster virus immunoglobulin G antibody.

- a. Day relative to start of study treatment (Day 1).
- b. From Day 86 through Day 365, if the subject flares as defined by protocol, begin rescue treatment period. See [Schedule of Activities for Rescue Treatment](#).
- c. Obtain written informed consent; for subjects aged under the legal age of majority (legal adulthood) in the subject's country, obtain written informed consent from legally acceptable representative/parent(s) or legal guardian, and informed assent from the patient (if age appropriate according to local regulations).

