### **5. STUDY TREATMENTS**

For this study, the investigational products are PF-04965842 and placebo. Enrolled subjects receive 12 weeks induction treatment of 200 mg PF-04965842 QD during an open-label run-in period. At the end of the 12 weeks, subjects responding to treatment as described in [Section 3](#) are randomized into the double-blinded, maintenance treatment period during which they receive 200 mg PF-04965842 QD, 100 mg PF-04965842 QD, or placebo (1:1:1 randomization ratio) for 40-weeks. The last dose of open label run-in treatment (200 mg) is administered at the Week 12 visit; subjects initiate administration of randomized blinded treatment the day after the Week 12 visit. In the event of loss of response during blinded treatment denoted as flare, defined as a loss of at least 50% of the EASI response at Week 12 and an IGA score of 2 or higher, subjects will enter a 12-week open-label rescue period and receive 200 mg PF-04965842 QD with concomitant topical therapy per SOC.

An investigator can temporarily interrupt dosing for up to a maximum of 28 consecutive days for a subject for safety reasons or while monitoring abnormal laboratory tests if the investigator judges that this is necessary ([Appendix 4](#)). The investigator should use their judgement with regard to unscheduled visits/laboratory/clinical assessments required to monitor the subject during this time-frame. If within this timeframe the investigator judges that it is safe to restart dosing, then the subject may restart investigational product. If the

investigator judges that it is not safe to restart dosing within this timeframe, then the subject must be permanently discontinued from treatment, have an End of Treatment visit and enter the 4-week follow-up period. Doses not taken for the reasons mentioned above do not constitute protocol deviations or medication errors and should not be considered dosing errors, but should be noted in the dosing log with the reason for reduced drug consumption clearly described.

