### **5.2. Rescue Treatment**

Subjects will be instructed to contact the site if they experience a significant worsening of their atopic dermatitis, such as a recurrence of pruritus, during the double-blind treatment period. Site staff will determine if the subject should return to the site for an unscheduled (see [Section 6.5.1](#)) or regularly scheduled visit (see [Section 6.3](#)). Subject will be reminded not to take study drug on the day of the site visit. At the visit (regular or unplanned) the subject will be assessed for flare, defined as a loss of at least 50% of the EASI response at Week 12 and an IGA of 2 or higher. Subjects who meet the definition of flare are to receive rescue treatment that day and enter an open-label rescue period during which they receive 12-weeks of 200 mg PF-04965842 QD with concomitant topical therapy per SOC. See [Section 5.2.1](#) for guidance on topical therapies.

After completing the rescue period, subjects are allowed to enter the LTE study B7451015, if eligible. If a subject discontinues prematurely or is not eligible or willing to participate in B7451015, then the subject enters the 4-week, untreated follow-up safety period. Refer to [Schedule of Activities for Rescue Treatment](#).

Subjects not meeting the definition of flare will continue on their blinded treatment. Physicians may continue to clinically evaluate for flare using the EASI and IGA assessments at their discretion.

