#### **6.5.1. Rescue Treatment - Flare Occurring at an Unplanned Visit (Rescue Visit 1, Day 1/Week 0 (±3 days))**

- Administer and score the Since Last Visit C-SSRS. For subjects meeting any of the criteria specified in [Section 7.5.1](#) a risk assessment by a qualified MHP should be done to determine whether it is safe for the subject to continue to participate in the trial;
- Administer PROs including: PtGA, DLQI (or CDLQI), POEM, HADS, EQ-5D-5L (or EQ-5D-Y in select countries), SF-36v2, Acute and FACIT-F (or Peds-FACIT-F). SF-36v2 will be completed by adult subjects only;
- Adolescents 12-17 years of age will not complete the SF-36v2. Adolescents 12-17 years of age will complete the CDLQI instead of the DLQI, the EQ-5D-Y in select countries instead of the EQ-5D-5L and Peds-FACIT-F instead of the FACIT-F;

- Review PSAAD daily completion (in selected countries) and pruritus NRS completion for this visit in the eDiary. Instruct the subject that the pruritus NRS completion will be collected daily in the eDiary from Days 1-15 during rescue treatment and then only on study visit days at the investigator site thereafter. PSAAD will be completed daily (in selected countries) in the eDiary from Day 1 through the EOS visit during rescue treatment. Review eDiary procedures with subject as necessary;
- Obtain weight for all subjects and height for adolescents only (12 to <18 years old);
- Conduct targeted physical examination;
- Obtain vital signs including pulse rate, blood pressure, respiratory rate and oral or tympanic temperature (after at least 5 minutes of rest);
- Perform a single 12-lead ECG;
- Conduct clinical evaluations including IGA, SCORAD, EASI and BSA (calculated in the EASI);
- Obtain fasting samples for laboratory testing: serum chemistry, hematology (including coagulation, RBC/WBC Indices, lymphocyte subsets and markers), lipid profile, and urinalysis;
-  
- Following one year of total exposure to study drug since the last TB test, all subjects in regions which are above a low risk for Tuberculosis (ie, >10/100,000 prevalence) will undergo tuberculosis (TB) testing. If so, ensure testing is performed as per [Section 7.3.4](#). A negative test result for tuberculosis is required for ongoing eligibility for study participation;

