5.2.2. Analyses for Longitudinal Continuous Data

Mixed-effect, repeated measures (MMRM) models will be used. Fixed effects for visit, treatment group, treatment-by-visit interaction (where treatment comparisons are relevant), disease severity at Study Baseline and randomization stratification factor will be included in the model. Visit will be modeled as a categorical covariate. Unstructured covariance matrix will be assumed for the model errors. Compound symmetry covariance matrix will be used if the model with unstructured covariance doesn't converge.

When modeling the change from baseline values, the variable for visit will start with the first post-baseline visit, and the actual baseline value will be included as a covariate. At each visit, estimates of least square mean (LSM) values and the pairwise LSM differences between the treatment groups will be derived from the model. The corresponding p-values and 95% confidence intervals will also be derived from the model.

For analyses where treatment comparisons are not relevant, the MMRM model will not have treatment as a factor and only estimates of the LSM values along with their 95% confidence intervals by visit will be reported.

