Appendix 2. Definition and Use of Visit Windows in Reporting

Visit windows will be used for efficacy variables, and for any safety lab data that display or summarize by study visit. For other endpoints (eg, ECG, vital signs), visit windows will be applied for summary statistics by study visits if required.

Visit Windows Applicable for Run-In and Blinded Phases

Visit Label	Target Day	Definition [Day window]
Screening		Days -28 to Day -1
Study Baseline	Day 1 (Day of first dose)	Last observation prior to and including day of first dose
Week 2	15	Days 2 to 22
Week 4	29	Days 23 to 43
Week 8	57	Days 44 to 71
Week 12	85	Days 72 to 99 but not beyond first randomized dosing date
Week 16	113	Days 100 to 155 but after first randomized date
Week 28	197	Days 156 to 239
Week 40	281	Days 240 to 323
Week 52	365	Days 324 to 379
Week 56	-	Days 380 to -

For the lab values, if the calculated study day for the labelled baseline visit is not study Day 1 but falls within 28 days before the start of the study dosing, then that data should be used for the baseline instead of leaving baseline missing.

For the other values, if the calculated study day for the labelled baseline visit is not study Day 1, but falls before the start of the study dosing, then that data should be used for the baseline instead of leaving baseline missing.

Visit Windows Applicable for Rescue Therapy Phase

Rescue Visit Label	Target Day*	Definition [Day window*]
Rescue Baseline	Day 1 (Day of first rescue dose)	Last dose of blinded treatment until Day 1
Rescue Week 2	15	Days 2 to 22
Rescue Week 4	29	Days 23 to 43
Rescue Week 8	57	Days 44 to 71
Rescue Week 12	85	Days 72 to 99
Rescue Week 16	-	Days 100 to -

- * Days are relative to Day 1 being the first day of rescue therapy.

If two or more visits fall into the same window, keep the one closest to the Target Day. If two visits are equaled distant from the Target Day in absolute value, the later visit should be used.

If there are more than one observations collected on the same day, the one with the latest time should be used.

Safety analysis may follow CaPS standards.

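### SAP Appendix 2 leaves roughly Days 87 to 99 in no visit window, so a subject who flares and starts rescue in that gap drops out of the change-from-Randomization-Baseline MMRMs

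*SAP*

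**What the plan says.** SAP Appendix 2 applies analysis windows to the efficacy variables. Week 12 (target Day 85) covers "Days 72 to 99 but not beyond first randomized dosing date". Week 16 (target Day 113) covers "Days 100 to 155 but after first randomized date". Where several visits share a window, the rule is: "If two or more visits fall into the same window, keep the one closest to the Target Day". Nothing says what happens to an observation that falls in no window.

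On timing, protocol Section 5 states that "subjects initiate administration of randomized blinded treatment the day after the Week 12 visit". Footnote b of the protocol's Schedule of Activities reads: "From Day 86 through Day 365, if the subject flares as defined by protocol, begin rescue treatment period". Section 5.2 allows flare to be assessed at an unscheduled visit and adds: "Subjects who meet the definition of flare are to receive rescue treatment that day". Section 6.5.1 has a full set of efficacy and patient-reported assessments taken at that visit, and Section 7.8 places them before dosing.

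On analysis, SAP 6.3.2 and 6.4.1 use the Randomization Baseline for visits after Week 12. SAP 5.2.2 says of the MMRM: "Visit will be modeled as a categorical covariate". SAP 5.3.2 treats FAS-RA values after entry to rescue as missing, and defends missing-at-random by conditioning on past and current EASI and IGA.

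**The concern.** The Week 12 window was cut at the first randomised dose, but the start of the Week 16 window was not moved to meet it. The qualifier on Week 16 can only narrow Days 100 to 155, when randomisation is late. It cannot open the window earlier.

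The days left unlabelled follow immediately after withdrawal of open-label drug. A subject rescued then has one post-randomisation assessment under blinded treatment, and that assessment has no label. A flare first found at a visit on Days 100 to 113 does have one. Inclusion therefore depends on how early response was lost.

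If placebo subjects flare earlier, which is expected although the documents give no flare rates, the worst early placebo outcomes are removed more often and the treatment difference would tend to shrink. These analyses are tested at a nominal 5% (SAP 5.1). In the EASI model, the current EASI value on which SAP 5.3.2 rests its missing-at-random argument is also lost.

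**Working it through.** **1. Reproduce the plan's boundaries.** The target days are 15, 29, 57, 85, 113, 197, 281 and 365 (SAP Appendix 2). The midpoints of adjacent targets are 22, 43, 71, 99, 155, 239 and 323. These match every interior window boundary, so Day 99/100 is the plain midpoint between 85 and 113. The cut at the first randomised dose was then added to the Week 12 side only.

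**2. Size of the gap.** The Week 12 visit is Day 85 ± 3 and the first randomised dose is one day later. Unlabelled days run from the day after that dose to Day 99.

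| Week 12 visit | First randomised dose | Unlabelled days | Length | First gap day to Day 113 |
|---|---|---|---|---|
| Day 82 | Day 83 | 84–99 | 16 | 29 days |
| Day 85 | Day 86 | 87–99 | 13 | 26 days |
| Day 88 | Day 89 | 90–99 | 10 | 23 days |

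**3. Path of one subject.** Take a flare and rescue on Day 90. The Day 90 assessment is in neither window. Values at Weeks 16, 28, 40 and 52 are post-rescue and missing. The subject has no row in the Randomization-Baseline MMRM. The Day 90 value survives only as Rescue Baseline in FAS-RE.

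**4. Size of each lost EASI value.** Entry requires EASI ≥ 16 (protocol 4.1). EASI-75 means a fall of at least 0.75 × 16 = 12. Flare requires half of that response to be lost (SAP 3.1): 0.5 × 12 = 6. Each lost value is a rise of at least 6 points.

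**5. Number of subjects: illustration only.** The documents give no flare rates. Assumptions:
- 200 per arm, no dropout, a gap of 13 days (13/7 weeks) counted from the start of randomised treatment;
- active medians 1.5 times placebo, the ratio used in the sample-size section;
- a share s = 0.5 to 1 of flares seen at an unscheduled visit the same day;
- Weibull event times with shape k, the family used in SAP Appendix 6.

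Subjects lost per arm = 200 × s × (1 − 2^(−((13/7)/median)^k)).

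Placebo, with each active arm in brackets:

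| Shape k | Placebo median 8 weeks | 16 weeks | 40 weeks |
|---|---|---|---|
| 0.7 | 22–44 (17–34) | 14–28 (11–22) | 8–16 (6–12) |
| 1 | 15–30 (10–20) | 8–15 (5–10) | 3–6 (2–4) |
| 1.5 | 7–15 (4–8) | 3–5 (1.5–3) | about 1 (under 1) |
| 2 | 4–7 (2–3) | 1–2 (under 1) | under 1 (under 1) |

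Worked cell, k = 1, median 16, s = 1: placebo 200 × (1 − 2^(−1.857/16)) = 15.5; active 200 × (1 − 2^(−1.857/24)) = 10.4. Placebo makes up 56% to 69% of those lost in each placebo comparison.

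**6. Analyses not affected.** The primary endpoint uses the flare date on the CRF (SAP 6.1.1.1), and the key secondary is also time to event. Binary endpoints count rescued subjects as non-responders (SAP 5.3.1). The Week 12 model uses run-in data and the Study Baseline. For PSAAD the effect is unclear, because Appendix 2 does not say how daily entries are averaged after Week 12.

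**The case against.** The best reply is that this is loose wording and not a rule to discard data. Taken literally, the Week 16 qualifier does almost nothing, since randomisation on or after Day 100 would be far outside the Day 85 ± 3 visit window. The author may have meant the first randomised dose to be the switch between Week 12 and Week 16. That may well be the intent, but it is not what the table says, and a programmer following it would leave these values out.

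A second reply is that the flare value is labelled Rescue Baseline. That label serves only FAS-RE and gives no entry to the FAS-RA model. The SAP is, however, uneven about which phase the first rescue day belongs to: Sections 5.3.1, 5.3.2, 6.2.1.1 and 6.7 treat it differently. Section 5.3.2, which governs these models, makes only values after rescue missing, so a pre-dose value should count. The unevenness is a reason to state this outright.

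Other points stand as limits. No scheduled visit falls in the gap, so only full flares seen at unscheduled visits within about two weeks of randomisation matter. The EASI model contains no IGA, so the missing-at-random argument is incomplete whatever the windows. In the other models neither score is present, and the issue is only outcome-related loss. The affected analyses are outside the testing hierarchy, and the likely direction is against the drug.

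**Conclusion.** The concern holds. As written, Appendix 2 leaves 13 days unlabelled nominally (10 to 16 across the visit window), and subjects who flare and are rescued in them are excluded from the Randomization-Baseline MMRMs because of their outcome. That conclusion follows from the text alone.

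The effect on the results is unknown. The illustrated loss depends on assumed medians, hazard shape and detection, and can be close to nil. The effect on the least-squares mean differences was not estimated. Greater loss on placebo is an expectation. The point should be corrected before unblinding, but it does not threaten the primary or key secondary conclusions.

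**What to change.** In SAP Appendix 2, define Week 16 as the day after the first randomised dose to Day 155. This leaves no unassigned days for any Week 12 visit from Day 82 to Day 88. The rest of the table can stay.

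Add the order of operations: remove post-rescue values first, then apply the closest-to-target rule, and keep the pre-dose flare assessment. The order matters. After a flare on Day 90, Rescue Week 4 (rescue Day 29) falls on Day 118, 5 days from target against 23 for the flare value. It would be selected and then set to missing.

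The cost is one line and a note, with no change to data collection. For some early leavers, including those who leave for reasons other than flare, a value up to 26 days before Day 113 (29 if the Week 12 visit was on Day 82) would stand for Week 16. The repair is also partial: flare values from unscheduled visits after an on-time visit in the same window (about Days 114–155, 198–239 and 282–323) still lose to the scheduled visit, although those subjects stay in the model.

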### **Lost to follow-up:**

All reasonable efforts must be made to locate subjects to determine and report their ongoing status. This includes follow-up with persons authorized by the subject as noted above. Lost to follow-up is defined by the inability to reach the subject after a minimum of 2 documented phone calls, faxes, or e-mails as well as lack of response by the subject to 1 registered mail

letter. All attempts should be documented in the subject's medical records. If it is determined that the subject has died, the site will use locally permissible methods to obtain the date and cause of death. If the investigator's use of a third-party representative to assist in the follow-up portion of the study has been included in the subject's (legally acceptable representative/parent(s) or legal guardian, as applicable) informed consent, then the investigator may use a sponsor-retained third-party representative to assist site staff with obtaining the subject's contact information or other public vital status data necessary to complete the follow-up portion of the study. The site staff and representative will consult publicly available sources, such as public health registries and databases, in order to obtain updated contact information. If, after all attempts, the subject remains lost to follow-up, then the last-known-alive date as determined by the investigator should be reported and documented in the subject's medical records.

Subjects may withdraw from the study at any time at their own request, or they may be withdrawn at any time at the discretion of the investigator or sponsor for safety (see also the [Withdrawal From the Study Due to Adverse Events](#) section) or behavioral reasons, or the inability of the subject to comply with the protocol-required schedule of study visits or procedures at a given study site. Subjects that discontinue study treatment will remain in the study and must have their end of treatment visit within 1 week after their last dose, and will then enter the 4 week follow up period with an End of Study visit 4 weeks after End of Treatment visit. See [Appendix 4](#) for Guidelines for Monitoring and Discontinuation.

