6. ANALYSES AND SUMMARIES

Treatment comparisons will only be displayed for the FAS-RA analysis set where it is relevant. Pairwise comparisons will be reported among the treatment groups. No treatment comparisons are relevant for the FAS-OL and FAS-RE analysis sets. Similarly, safety data displays will be by treatment group only for SAF-RA and not for SAF-OL or SAF-RE.

A summary of analyses for clinical efficacy endpoints is provided in [Appendix 1](#). Visit windows to be used for all efficacy analyses and some relevant safety analyses are detailed in [Appendix 2](#).

Efficacy and PRO data collected at the Week 16/Week 56 follow-up visits or at the Rescue Visit Week 16 follow-up visit will be displayed in listings only, and will not be part of any analyses, unless specifically noted otherwise.

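### SAP Appendix 2 sets no last-dose limit, so by-visit lab tables can show an early stopper's untreated follow-up value as Week 16, 28, 40 or 52

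*SAP*

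**What the plan says.** SAP Appendix 2 makes the windows binding for labs shown by visit: "Visit windows will be used for efficacy variables, and for any safety lab data that display or summarize by study visit". The relevant windows are Week 12, "Days 72 to 99 but not beyond first randomized dosing date"; Week 16, "Days 100 to 155 but after first randomized date"; Week 28, "Days 156 to 239"; Week 40, "Days 240 to 323"; and Week 52, Days 324 to 379. A follow-up label (Week 56) exists only from Day 380. The Week 12 and Week 16 windows carry a condition on the first randomized dose or date. None carries a condition on the last dose. Within a window, "If two or more visits fall into the same window, keep the one closest to the Target Day", with ties going to the later visit.

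Under Protocol 6.6, a subject who stops treatment has an end-of-treatment visit within a week of the last dose and "will then enter the 4 week follow up period with an End of Study visit 4 weeks after End of Treatment visit". Protocol 6.3.5 and 6.4.1 draw chemistry, hematology and lipids at both visits, and 6.4.1 gives the follow-up visit ±3 days.

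SAP 6 restricts to listings the "Efficacy and PRO data collected at the Week 16/Week 56 follow-up visits" and the corresponding rescue follow-up data. Safety labs are not named. SAP 6.7 censors safety data at the start of rescue and states no censoring for early termination. SAP 6.7.2 describes the randomized-phase lab change analysis as running up to when randomized dosing ends.

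**The concern.** The study-day windows work for completers, whose follow-up visit lands after Day 380. For someone who stops early they do not: the untreated visit falls inside a window carrying an on-treatment label. Protocol 1.3 gives a terminal half-life of 2.8 to 5.0 hours on repeat dosing, so a lab about 4 weeks after stopping is an off-drug value.

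The affected subjects include those stopped for laboratory reasons under Protocol Appendix 4 (platelets, neutrophils, lymphocytes, hemoglobin, liver tests, creatinine). Protocol 1.2.4 reports dose-dependent platelet decreases in Phase 2b, and 1.5 names reduced platelet count as a risk. If recovered values are tabulated as Week 28 on the assigned dose, the by-visit means and changes move toward no effect in any arm with such stops.

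**Working it through.** **The plan's own figures.** The window limits are midpoints between adjacent target days. With targets 15, 29, 57, 85, 113, 197, 281, 365 and 393 (365 + 28 for follow-up), the midpoints are 22, 43, 71, 99, 155, 239, 323 and 379. These match Appendix 2 exactly.

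**Inputs for the blinded phase.** Week 12 visit on Day 85 and first randomized dose on Day 86 (Protocol 5 and 6.3.1). Early ET visits on Days 87 to 364, which is 364 − 87 + 1 = 278 possible days. EOS day = ET day + 28, varied from +25 to +31. The count takes ET and EOS as the only labs competing within a window.

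**Mislabelling.** The EOS lab takes an on-treatment label if ET + 28 ≤ 379, so ET ≤ 351. That is 351 − 87 + 1 = 265 of 278 days. With +25 the limit is Day 354 (268 days); with +31 it is Day 348 (262 days).

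**Replacement.** Both labs must share a window, and EOS must be at least as close to target T:

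|ET + 28 − T| ≤ |ET − T|, which reduces to ET ≤ T − 14.

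| Window | Target | T − 14 | ET days with replacement | Count |
|---|---|---|---|---|
| Week 16 (from Day 100) | 113 | 99 | none | 0 |
| Week 28 (from Day 156) | 197 | 183 | 156–183 | 28 |
| Week 40 (from Day 240) | 281 | 267 | 240–267 | 28 |
| Week 52 (from Day 324) | 365 | 351 | 324–351 | 28 |

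Total 84; 84/278 = 30%. At +25 the total is 88 (one day in Week 16 and 29 in each of the other three), 88/278 = 32%. At +31 it is 26 + 26 + 25 = 77, 77/278 = 28%.

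Example: ET on Day 170 is 27 days from target 197, and EOS on Day 198 is 1 day from it. The Week 28 value is the untreated one and the stopping value is dropped. For ET on Day 183, EOS is Day 211; both are 14 days from target, and the tie rule keeps the untreated value.

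**Days 87–99.** With first randomized dose on Day 86, an ET lab on these days fits neither the Week 12 nor the Week 16 window. Its EOS lab (Days 115–127) is labelled Week 16.

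**Run-in and rescue.** ET on Days 2–71 gives EOS on Days 30–99, labelled Week 4, 8 or 12 (or the rescue equivalent). No window up to Day 99 is longer than 28 days, so two labs 28 days apart cannot share one and replacement does not occur. At +25 it occurs for two ET days, 44 and 72.

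**Completers.** EOS on Days 387–399 (362 + 25 to 368 + 31) is always Week 56.

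**The case against.** The strongest reply is that the body of the SAP already limits the data. SAP 6.7.2 confines the randomized-phase change analysis to the end of dosing, and SAP 6.7 confines the open-label safety set to the first 12 weeks of treatment. On that reading Appendix 2 only labels data already in scope. This shows an on-treatment intent, but it is not an assignment rule: an EOS lab that Appendix 2 has labelled Week 28 looks in scope. Appendix 2 also says safety analysis may follow the sponsor's standards (CaPS), which could hold a cut-off. Those standards are not in the documents, and a permissive sentence does not displace a mandatory one.

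Four stronger readings are tempting, and the documents do not support them.

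- **That the abnormal value vanishes from the safety report.** SAP 6.7 runs abnormality displays across the subject's whole study experience and provides listings. Protocol 7.6.2 and 8.2.2 have clinically significant findings, and results leading to discontinuation from the study, recorded as adverse events.
- **That 30% of early stoppers are affected.** It is a share of calendar days. No dropout rate is given, and subjects who flare leave the blinded ET path for rescue.
- **That run-in and rescue lose stopping values in the same way.** At ET + 28 they show mislabelling only.
- **That the discarded ET lab is always an on-drug value.** The ET visit may come up to a week after the last dose, and Protocol Appendix 4 allows an interruption of up to 28 days before permanent discontinuation.

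**Conclusion.** The point holds within these limits. Followed literally, Appendix 2 labels the untreated follow-up lab as Week 16, 28, 40 or 52 for nearly every early ET day in the blinded phase (265 of 278), and discards the ET lab in its favour on 84 of those days, all in the Week 28, 40 and 52 windows. This rests on the nominal Day 86 start of randomized dosing and on EOS at ET + 28. The ±3-day tolerance moves the replacement share only between 28% and 32%.

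The damage is confined to by-visit lab summaries and change-from-baseline displays, where it conflicts with the scope that SAP 6.7.2 sets. The primary and key secondary analyses are untouched. The number of subjects affected, and any imbalance between arms, cannot be derived from the documents. It is more than a missing detail, because the written rule gives the wrong value when applied as written.

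**What to change.** Add one rule to SAP Appendix 2. For by-visit safety displays, only labs (and ECG and vital signs when windowed) taken no later than 7 days after the last dose of that period are eligible for the Week 2–52 and Rescue Week 2–12 windows. EOS visits and any later assessments go in a separate Follow-up row, whatever the study day.

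Seven days is the allowance in Protocol 6.6 for the end-of-treatment visit. EOS comes at least 0 + 25 = 25 days after the last dose, so none qualifies: mislabelled ET days fall from 265 to 0 and replacements from 84 to 0. The 28-day lag used for adverse events in SAP 3.5.1 would not do. With ET on the last-dose day, an EOS lab 25 to 28 days later would still qualify.

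The cost is one sentence and one programming condition. Counts at later visits become slightly smaller, and an ET lab taken more than 7 days after the last dose, for example after a dosing interruption, moves to the Follow-up row. The rule does not give ET labs on Days 87–99 a window; that needs its own decision.
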